9.2. PROTOCOL DEVIATIONS AND ELIGIBILITY

Table 14.1.4.1: Protocol deviations: Summary of major protocol deviations

Frequency tabulation per treatment group (including the overall total) of major protocol deviations.

Population: safety analysis set

Listing 16.2.2.1: Major protocol deviations

Listing per treatment group and per subject showing all major protocol deviations that occurred during the study.

Population: safety analysis set.

Listing 16.2.2.2: Eligibility criteria: Violations

Listing per treatment group and per subject showing only the violated selection criteria for subjects treated (inclusion criteria not met, and exclusion criteria met), if any.

Population: safety analysis set.

Listing 16.2.2.3: Eligibility: Final statements

Listing per treatment group and per subject showing the eligibility statements at Screening and Day 1 (answers to the question “Did the subject meet all inclusion criteria and did not meet any exclusion criteria?”).

Population: safety analysis set

9.3. SUBJECTS EXCLUDED FROM ANALYSIS PART

Note that for the PK data there is a specific PK data handling listing. PK is therefore not included in this section.

Listing 16.2.3.1: Subjects excluded from safety and full analysis sets

Listing of all subjects who were not treated due to any reason, showing them categorized as not treated subjects who were not randomized at all, and not treated subjects who were randomized (if randomization applies).

The study completion or discontinuation status, and any available reasons or specifications will also be printed next to each subject.

In the exceptional case a same subject participated more than once in this study due to any reasons (like first as a reserve subject not treated, and then again as a treated subject), the multiple participations of such a subject will be flagged and mentioned in this listing.

Population: all screened subjects (only subjects excluded from safety analysis set will be listed).

9.4. DEMOGRAPHICS AND BASELINE CHARACTERISTICS**9.4.1. Parameters**

The following parameters will be presented:

- Gender;
- Age (years) at the date of ICF signature;
- Year of birth: only listed;
- Date of study participation ICF signature: only listed;
- [REDACTED];
- [REDACTED];
- Race;
- Ethnicity;
- Height (cm) at baseline;
- Weight (kg) at baseline;
- Body mass index (BMI) at baseline;
- BMI categories at baseline:
 - ≤ 18.5 kg/m²

-]18.5, 25.0] kg/m²
-]25.0, 30.0] kg/m²
- > 30.0 kg/m²;
- Systolic blood pressure (mmHg) at baseline: only listed;
- Diastolic blood pressure (mmHg) at baseline: only listed;
- Heart rate (bpm) at baseline: only listed;
- Temperature (°C) at baseline: only listed;
- Childbearing potential for females: yes, no;
- Alcohol consumption: never, current, former;
- Nicotine consumption: never, current, former;
- Caffeine consumption: never, current, former.

Parameters mentioning ‘at baseline’ imply the selection of the last available result before the first study drug administration.

9.4.2. Analysis

Table 14.1.3.1: Demographic data: Descriptive statistics and tabulation

Continuous parameters: descriptive statistics per treatment group (including the overall total).

Categorical parameters: frequency tabulation per treatment group (including the overall total).

Population: safety analysis set.

Listing 16.2.4.1: Demographic data and baseline characteristics

Listing per treatment group and per subject of all demographic and baseline characteristic parameters.

Population: safety analysis set.

Listing 16.2.4.2: Substance use

Listing per treatment group and per subject of alcohol, nicotine and caffeine consumptions.

Population: safety analysis set.

9.5. BASELINE DISEASE CHARACTERISTICS

9.5.1. Parameters

- Duration of AD (years) = $\frac{(\text{date of signing ICF}) - (\text{date of initial diagnosis}) + 1}{365.25}$.
If the date of initial diagnosis is incomplete, then the following rules will be applied:
Missing day: use the first of the month.
Missing month: use January;
- Duration of AD, categorized as:
 - < 1 year,
 - [1, 2[year,
 - [2, 5[year,
 - [5, 10[year,
 - [10, 20[year,
 - ≥ 20 year;
- Date of initial diagnosis: only listed;
- Age at time of initial diagnosis = $\frac{(\text{date of initial diagnosis}) - (\text{date of birth}) + 1}{365.25}$ (as day and month of the date of birth are not recorded in the database, this will be imputed to the 1st of July), categorized as:
 - < 18 years,
 - [18, 50[years,
 - ≥ 50 years;
- [REDACTED];
- [REDACTED];
- [REDACTED];
- [REDACTED];
- Use of the following therapy (Yes/No):
 - Biologics therapy;
 - Non-biologic systemic therapy;
 - Phototherapy;
 - Topical treatment for AD;
- Any other AD: only listed.

9.5.2. Analysis

Table 14.1.3.2: Screening and baseline disease characteristics

Continuous parameters: descriptive statistics per treatment group (and overall).

Categorical parameters: frequency tabulation per treatment group (and overall).

Population: safety analysis set.

Listing 16.2.4.3: Screening and baseline disease characteristics

Listing per treatment group and per subject of all baseline disease characteristic parameters (date of initial diagnosis, duration of AD (flag the imputed durations), previous treatments for AD, other atopic disease), [REDACTED] [REDACTED]

Population: safety analysis set.

9.6. MEDICAL HISTORY AND CONCURRENT DISEASES**Table 14.1.3.3: Medical history: Tabulation**

Frequency tabulation per treatment group (and overall) of the system organ classes and preferred terms, selecting only medical conditions no longer present at the start of the study i.e. start of screening period.

Population: safety analysis set.

Table 14.1.3.4: Concurrent diseases: Tabulation

Frequency tabulation per treatment group (and overall) of the system organ classes and preferred terms, selecting only medical conditions still present at the start of the study i.e. start of screening period.

Population: safety analysis set.

Listing 16.2.4.4: Medical history

Listing per treatment group and per subject of the reported medical conditions no longer present at the start of the study i.e. start of screening period (including system organ class and preferred term from MedDRA coding dictionary).

Population: safety analysis set.

Listing 16.2.4.5: Concurrent diseases

Listing per treatment group and per subject of the reported medical conditions still present at the start of the study i.e. start of screening period (including system organ class and preferred term from MedDRA coding dictionary).

Population: safety analysis set.

9.7. PRIOR AND CONCOMITANT THERAPIES

9.7.1. Coding of Reported Terms

All prior and concomitant medications terms are expected to be coded using the WHO-DRUG coding dictionary (version March 2018 or later).

In the tables, the generic term will be used. The ATC classification will be used for analysis. Multiple records of the same generic term for the same subject with the same categorization will be counted only once. The table will therefore present subjects, not occurrences.

9.7.2. Categorization for Timing

All prior and concomitant therapy records will be categorized as follows, considering their dates:

- Prior only: when the record ended before the first study drug administration date.
- Concomitant only: when the record started on the same date or after the first study drug administration date until the last study drug administration + 30 days.
- Prior and concomitant: when the record started before the date of the first study drug administration, and ended on a date after the first study drug administration (or on the same date) or continued.

Records without a start date are assumed to have started before the date of the first study drug administration (records without an end date are assumed to be ongoing).

When the start or end dates of the prior and concomitant therapy records are incomplete, the date of the first study drug administration will be considered to the same level of information provided by the incomplete dates in order to categorize these records. This means a record only having month and year information will be categorized comparing only to the month and the year of the first study drug administration. The CRF question “Did the concomitant medication start prior to the first dose of study treatment?” will be also used for the categorization of the medication, if needed.

9.7.3. Calculation of the Relative Days

For both the start and the end dates of the concomitant therapy records, their day relative to the day of the first study drug administration will be calculated as described in section 5.4 of this SAP (calculation of relative days).

The relative day for a missing start date will be set to missing.

The relative day for an incomplete start or end date will be set to missing.

The relative day for a missing end date will be calculated up to the subject’s date of last contact in study, and will be printed as ‘>X days’.

9.7.4. Analysis

Table 14.1.3.5: Prior therapies: Tabulation

Frequency tabulation per treatment group (and overall) of the ATC 4 classes and generic terms. Only therapies defined above as ‘prior only’ or as ‘prior and concomitant’ are to be included.

Population: safety analysis set.

Table 14.1.3.6: Concomitant therapies: Tabulation

Frequency tabulation per treatment group (and overall) of the ATC 4 classes and generic terms. All therapies defined above as ‘concomitant only’ or ‘prior and concomitant’ are to be included.

Population: safety analysis set.

Listing 16.2.4.6: Prior and concomitant therapies

Listing per treatment group and per subject of all prior and concomitant therapy records, also showing their categorized timing as prior only, concomitant only or prior and concomitant.

When these records are linked to medical history or adverse events, these additional details (reported term of the medical history condition(s) or reported term of the adverse event(s), including their record ID numbers) will be printed as well.

Population: safety analysis set.

Listing 16.2.4.7: Prior and concomitant TCS/TCI therapies against atopic dermatitis

Same as [Listing 16.2.4.6](#), only selecting TCS/TCI medications (i.e., Was this a TCS/TCI medication?="Yes").

Population: safety analysis set.

Listing 16.2.4.8: Concomitant intake of rescue atopic dermatitis medications

Same as [Listing 16.2.4.6](#), selecting only rescue medications records (i.e., indication="Rescue AD medication").

Population: safety analysis set.

9.8. EXPOSURE TO STUDY MEDICATION AND COMPLIANCE

9.8.1. Derivations

A total of 4 treatment days with s.c. doses (including loading dose on day 1) are to be received by the subject.

Total treatment duration (days) = last dose of study medication date – first dose of study medication date + 1 day.

In addition, the number (%) of subjects who received >4, 4, 3, 2, 1 treatment days with s.c. injections will be tabulated.

9.8.2. Analysis

Table 14.1.5.1: Use of study medication: Descriptive statistics

Descriptive statistics per treatment group (and overall) of the total treatment duration (days).

Population: safety analysis set.

Table 14.1.5.2: Use of study medication: Tabulation of the number of injections received

Frequency tabulation per treatment group (and overall) of the number of treatment days with s.c. injections received: >4, 4, 3, 2, 1.

Population: safety analysis set.

Listing 16.2.5.1: Study drug administration

Listing per treatment group and per subject of all records related to the administration of study drug.

Population: safety analysis set.

Listing 16.2.5.2: Cross-treated subjects

Listing of subjects who took incorrect study medication (from another randomization group) for at least part of the treatment period, all prime therapy records are to be included to provide an overview of the amount of cross-treatment relative to the total treatment period. Results are to be presented by treatment and subject.

Population: safety analysis set.

Listing 16.2.5.3: Subjects for whom the injections were not administered per protocol

Listing of subjects who did not receive injection per-protocol (i.e. loading dose was not provided at day 1 or provided at another time point will be listed; reason for not providing the dose will be listed as well). Results are to be presented by treatment and subject.

Population: safety analysis set.

10. ANALYSIS OF EFFICACY AND DEFINITION OF ANALYSIS TLFS

The efficacy outputs will be generated using FAS.

10.1. DEFINITIONS, DERIVATION RULES AND PRESENTATION OF EFFICACY PARAMETERS

10.1.1. [REDACTED]

10.1.1.1. [REDACTED]

[REDACTED]

[REDACTED]

[REDACTED]

[REDACTED]

[REDACTED]

[REDACTED]

10.1.1.2. Tables

Table 14.2.1.1: [REDACTED]

[REDACTED]

Population: full analysis set.

Table 14.2.1.4: [Redacted]

[Redacted Table Content]

[Redacted Table Content]

[Redacted Table Content]

[Redacted Table Content]

Population: full analysis set.

Table 14.2.1.5: [Redacted]

[Redacted Table Content]

[Redacted Table Content]

[Redacted Table Content]

Table 14.2.1.6: [Redacted]

[Redacted Table Content]

Population: full analysis set.

10.1.1.3. Figures

Figure 14.2.1.5: [Redacted]

Population: full analysis set.

Figure 14.2.1.17: [Redacted]

[Redacted]

Population: full analysis set.

10.1.1.4. Listings

Listing 16.2.6.1: [Redacted]

[Redacted]

Population: full analysis set.

10.1.2. [Redacted]

10.1.2.1. Derivations

[Redacted]

[Redacted]

10.1.2.2. Tables

Table 14.2.1.8: [Redacted]

[Redacted]

[Redacted]

Population: full analysis set.

[Redacted]

10.1.2.3. Figures

No figure will be provided for this parameter.

10.1.2.4. Listings

Listing 16.2.6.2: [REDACTED]

[REDACTED]

Population: full analysis set.

10.1.3. [REDACTED]

10.1.3.1. Derivations

[REDACTED]

[REDACTED]

[REDACTED]

10.1.3.2. Tables

Table 14.2.1.9: [REDACTED]

[REDACTED]

Population: full analysis set.

Table 14.2.1.11: [REDACTED]

[REDACTED]

Population: full analysis set.

10.1.3.3. Figures

Figure 14.2.1.15: 

Population: full analysis set.

Figure 14.2.1.17: 

Same figure as

[REDACTED]

Population: full analysis set.

10.1.3.4. Listings

Listing 16.2.6.3: [REDACTED]

[REDACTED]

Population: full analysis set.

10.1.4. [REDACTED]

10.1.4.1. Derivations

[REDACTED]

[REDACTED]

10.1.4.2. Tables

No table will be provided for this parameter.

10.1.4.3. Figures

No figure will be provided for this parameter.

10.1.4.4. Listings

Listing 16.2.6.4: [REDACTED]

[REDACTED]

Population: full analysis set.

10.1.5. [REDACTED]

10.1.5.1. Derivations

[REDACTED]

[REDACTED]

[REDACTED]

[REDACTED]

10.1.5.2. Tables

No table will be provided for this parameter.

10.1.5.3. Figures

No figure will be provided for this parameter.

10.1.5.4. Listings

Listing 16.2.6.5: [REDACTED]

[REDACTED]

Population: full analysis set.

10.1.6. [REDACTED]

10.1.6.1. Derivations

[REDACTED]

[REDACTED]

- [REDACTED]
- [REDACTED]
- [REDACTED]

[REDACTED]

10.1.6.2. Tables

No table will be provided for this parameter.

10.1.6.3. Figures

No figure will be provided for this parameter.

10.1.6.4. Listings

Listing 16.2.6.6: [REDACTED]

[REDACTED]

Population: full analysis set.

10.1.7. [REDACTED]

10.1.7.1. Derivations

[REDACTED]

[REDACTED]

- | [REDACTED]
- | [REDACTED]
- | [REDACTED]
- | [REDACTED]
- | [REDACTED]

[REDACTED]

10.1.7.2. Tables

Table 14.2.1.19: [REDACTED]

[REDACTED]

Population: full analysis set.

10.1.7.3. Figures

Figure 14.2.1.37: [Redacted]

[Redacted]

Population: full analysis set.

10.1.7.4. Listings

Listing 16.2.6.7: [Redacted]

[Redacted]

Population: full analysis set.

Listing 16.2.6.8: [Redacted]

[Redacted]

Population: full analysis set.

10.1.8. [Redacted]

10.1.8.1. Derivations

[Redacted]

[Redacted]

[Redacted]

[Redacted]

10.1.8.2. Tables

No table will be provided for this parameter.

10.1.8.3. Figures

No figure will be provided for this parameter.

10.1.8.4. Listings

[REDACTED]

[REDACTED]

[REDACTED]

10.1.9. [REDACTED]

10.1.9.1. Derivations

[REDACTED]

[REDACTED]

[REDACTED]

10.1.9.2. Tables

No table will be provided for this parameter.

10.1.9.3. Figures

No figure will be provided for this parameter.

10.1.9.4. Listings

[REDACTED]

[REDACTED]

[REDACTED]

11. ANALYSIS OF PHARMACOKINETICS AND DEFINITION OF ANALYSIS TLFs

11.1. DEFINITIONS, DERIVATION RULES AND PRESENTATION OF PK PARAMETERS

11.1.1. Available Data

Compound: MOR106 in serum (free drug levels).

11.1.2. PK Parameters and Derivation Rules

No PK parameters will be derived.

11.1.3. PK Derivation Rules

- Time deviation:
 - The actual sampling time will be used for graphical presentation of the individual data.
- Handling of BLOQ values:
 - Concentration BLOQ will be imputed according to the rules mentioned in section [7.8](#).
 - If the concentrations before the first quantifiable concentration time point is BLOQ, the concentration will be set to 0.
 - If the concentrations after the last quantifiable concentration time point is BLOQ, the concentration will be set to missing.
 - If there are embedded BLOQ values between quantifiable concentrations after the last dose on Day 43, these BLOQ values will be set to missing.
 - If there is a quantifiable concentration after 2 consecutive BLOQ values at the end of the profile after the last dose on Day 43, this quantifiable concentration will be set to missing.

Excluded data will be discussed in the PK Data Review (Appendix [16.1](#)) and flagged in the TLFs.

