7.3. CALCULATION AND PRESENTATION OF DESCRIPTIVE STATISTICS

Any descriptive statistics (and summary graphics) for continuous parameters will be printed only when the number of observations is two or more, except for PK analysis where specific rules are described below. Single observations will only be listed.

In the general subject information, efficacy and safety parts of the analysis, descriptive statistics will include:

- the number of non-missing observations (n);
- the arithmetic mean;
- the standard error (SE);
- the standard deviation (SD);
- the median;
- the minimum and maximum values;
- 95% confidence interval of the mean (only when requested).

For each parameter concerned, the number of decimal places printed for all descriptive statistics will be the same maximum number of decimals of the actual analysis values of the parameter, except:

- mean, median, confidence interval of the mean: one more decimal place;
- SD, SE: two more decimal places.

For PK part of the analysis, descriptive statistics will include:

- the number of non-missing observations (n);
- the number of data points above the limit of quantification (only applicable for concentrations);
- the arithmetic mean;
- the standard error (SE)
- the standard deviation (SD)
- the median;
- the minimum and maximum values;
- the coefficient of variation (CV%)
 - = 100 x (standard deviation/arithmetic mean);
- the geometric mean
 - = exp(arithmetic mean of ln-transformed data);
- the geometric coefficient of variation (geometric CV%)
 - = 100 x $\sqrt{e^{(\text{standard deviation of ln-transformed data})^2} - 1}$

If less than 50% of the subjects have quantifiable values, only the number of subjects with data, number of data points above the lower limit of quantification (LLOQ), the arithmetic mean, median, minimum, and maximum will be presented with the original calculated value. The other descriptive statistics will be listed as “NC” (not calculated).

If the calculated mean is below the lower limit of quantification (BLOQ), then it will be presented as “BLQ”.

The concentration levels will be presented in the original unit. Concentrations will be presented with:

- 2 decimals for values < 10
- 1 decimal for values > 10 and < 1000
- No decimals for value > 1000.

The descriptive statistics should be rounded to the same number of decimals as the individual values.

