7.8. HANDLING OF VALUES BELOW OR ABOVE A THRESHOLD

- In the general subject information and in the safety part of the analysis: when results or normal limits of continuous parameters are expressed in the database as being below or above a detection limit (e.g. “<4”, “>1000”) and not available in pure

numerical form, the analysis value will be the value of the detection limit itself plus or minus one precision unit (e.g. 3, 1001, respectively). The values before this imputation will only be shown in listings.

- In the PK and PD [REDACTED] parts of the analysis:
 - o Values below the quantification limit will be imputed by 0 for the calculation of descriptive statistics, PK analyses and graphical presentation except for the geometric mean and the geometric CV, where it will be imputed as LLOQ/2.
 - o Values below the quantification limit will be listed as “BLQ”.

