8.2.1. Changes before Database Lock and Justification

Per Sponsor's decision:

- ECG parameters normal ranges will be different to the ones mentioned in protocol to be consistent with other Sponsor's studies.
- For laboratory statistical analyses, CTCAE version 4.03 will be used instead of version 5.0 to be consistent with other Sponsor's studies.
- FAS population definition will be updated to be the same as the safety analysis set (due to the type of subjects and disease, it is not anticipated to have a difference between these populations).
- The safety analyses will be based on the randomized treatment and not on the actual treatment (cf. section 7.3.8 of the protocol).

As a consequence of early termination of MOR106 development in atopic dermatitis:

- Per Protocol analysis set will not be defined as no analyses will be performed on this set.
- The Primary Analysis will not be conducted as mentioned in the protocol.
- [REDACTED]
- [REDACTED]
- [REDACTED]
- Time-to-event analysis will not be performed
- [REDACTED]
- [REDACTED]

- [REDACTED]
- Terminal half-life $t_{1/2}$ will not be derived as mentioned in the protocol.
- [REDACTED]

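### SAP 7.8 and 11.1.3 treat the same below-quantification MOR106 concentrations differently and neither takes precedence; under 11.1.3 the affected visit means are biased upward

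*SAP*

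**What the plan says.** SAP 7.8 gives the general rule for the PK part: "Values below the quantification limit will be imputed by 0 for the calculation of descriptive statistics, PK analyses and graphical presentation". The geometric mean and geometric CV are excepted and use LLOQ/2.

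SAP 11.1.3 begins by referring BLOQ concentrations back to 7.8. It then adds rules that depend on where the value falls in the subject's profile:

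- Leading: "If the concentrations before the first quantifiable concentration time point is BLOQ, the concentration will be set to 0".
- Trailing: "If the concentrations after the last quantifiable concentration time point is BLOQ, the concentration will be set to missing".
- Embedded: "If there are embedded BLOQ values between quantifiable concentrations after the last dose on Day 43, these BLOQ values will be set to missing".
- A further bullet sets to missing a quantifiable value that follows two consecutive BLOQ values at the end of the profile, after the Day 43 dose.

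Two display rules in SAP 7.3 also bear on this. One opens "If less than 50% of the subjects have quantifiable values, only the number of subjects with data" and goes on to list the few statistics still printed, with the rest shown as NC. The other opens "If the calculated mean is below the lower limit of quantification" and has such a mean printed as BLQ.

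On parameters, SAP 11.1.2 states "No PK parameters will be derived", and SAP 8.2.1 says the terminal half-life "will not be derived as mentioned in the protocol". The concentrations are summarised by visit in Table 14.2.2.1 (SAP 11.1.4).

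**The concern.** A trailing BLOQ record is 0 under one section and missing under the other. The SAP does not call the 11.1.3 bullets exceptions to 7.8, confine them to parameter derivation or state an order. Two programmers could therefore produce different versions of Table 14.2.2.1 from the same text, both compliant.

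The choice also has a direction. Setting BLOQ values to missing removes only the lowest values. SAP 7.1.1 does not impute missing values, so the visit mean then describes only subjects who still have measurable drug. Serum concentration through Day 169 is a secondary endpoint (SAP 2.3.2), and sampling continues for 16 weeks after the treatment period, which is where trailing BLOQ values are most likely. A full-course mean plot under SAP 8.1.8 would be affected in the same way. The trailing rule has no Day 43 limit, so it could also remove troughs up to Day 57 in a subject who becomes and stays BLOQ on treatment.

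**Working it through.** The plan states no figure on this point, so there is none to reproduce.

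**1. The rules side by side**

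| BLOQ record | 7.8, arithmetic | 7.8, geometric | 11.1.3 |
|---|---|---|---|
| Leading | 0 | LLOQ/2 | 0 |
| Embedded, after Day 43 dose | 0 | LLOQ/2 | missing |
| Trailing | 0 | LLOQ/2 | missing |

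The leading rule conflicts only for geometric statistics. SAP 7.3 defines the geometric mean through ln-transformed data, and ln(0) is undefined. This can matter at the Day 1 one-hour sample.

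**2. Do the bullets serve another purpose?** No PK parameter or half-life is derived, and population PK is described and reported separately (SAP 8.1.8). Within this SAP the bullets can therefore act only on concentration tables and plots.

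**3. 11.1.3 mean against 7.8 mean.** Let n subjects be sampled at a visit, k BLOQ values be set to missing, and S be the sum of the quantifiable values. The 7.8 mean is S/n and the 11.1.3 mean is S/(n-k), so the ratio is n/(n-k). BLOQ values left at 0 do not change S, so the ratio holds when only some BLOQ values are removed. With the planned n = 40 on MOR106:

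- k = 1: 40/39 = 1.026 (+2.6%)
- k = 4: 40/36 = 1.11 (+11%)
- k = 10: 40/30 = 1.33 (+33%)
- k = 20: 40/20 = 2.00 (+100%)

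**4. Each rule against the true mean.** Take a visit where all BLOQ values are trailing or embedded after Day 43. Let f = k/n, let Mq be the mean of the quantifiable values, and let m be the true mean of the BLOQ values, with 0 ≤ m < LLOQ. The true mean is (1-f)Mq + f·m.

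- Error of 11.1.3: Mq minus the true mean = f(Mq - m). It is too high, by between f(Mq - LLOQ) and f·Mq.
- Error of 7.8: (1-f)Mq minus the true mean = -f·m. It is too low, by less than f·LLOQ.
- Example, f = 0.25 and Mq = 3 LLOQ: 11.1.3 is too high by 0.25 × (3-1) = 0.50 to 0.25 × 3 = 0.75 LLOQ; 7.8 is too low by less than 0.25 LLOQ.
- The 11.1.3 error is the larger whenever Mq > 2m, which is guaranteed once Mq ≥ 2 LLOQ.

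**5. Illustration under assumptions.** The documents give no distribution, so assume lognormal concentrations, LLOQ = 1 unit, log-SD s from 0.5 to 1.2 and BLOQ share f from 0.10 to 0.75. Set μ = -s·z(f), with z(f) the standard normal f-quantile, so that a share f lies below LLOQ. The true mean is exp(μ + s²/2), the 7.8 mean is that times Φ(s + μ/s), and the 11.1.3 mean is the 7.8 mean divided by (1-f). For s = 0.8 and f = 0.25: true 2.36, 7.8 gives 2.20 (-7%), 11.1.3 gives 2.93 (+24%). Over s = 0.5, 0.8 and 1.2:

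| f | 11.1.3 error | 7.8 error |
|---|---|---|
| 0.10 | +7% to +10% | -4% to -1% |
| 0.25 | +17% to +29% | -12% to -3% |
| 0.50 | +38% to +77% | -31% to -12% |
| 0.75 | +72% to +180% | -57% to -30% |

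The 7.8 rule is the closer in all twelve combinations. Geometric means behave similarly: at s = 0.8 and f = 0.50 the true value is 1.00, LLOQ/2 gives 0.97 and set-to-missing gives 1.89.

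**6. The 7.3 display rules.** Where every BLOQ value at a visit has been set to missing, the mean of the remainder cannot be below LLOQ, so the BLQ display is never reached. The 50% rule becomes ambiguous. With n = 40 and k = 24, 16/40 = 40% gives NC if all sampled subjects count, but 16/16 = 100% gives full statistics if missing values are dropped first.

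**The case against.** The strongest reply is that the texts can be reconciled. The 11.1.3 bullets sit under a heading on PK derivation, follow a sentence adopting 7.8, and look like remnants from when a half-life was planned. That is a plausible reading, but 11.1.3 does not state it, and it leads to the same edit.

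Several limits on the concern stand:

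- The percentages in step 3 compare two rules; they are not bias against the truth. The 7.8 mean is itself low, and by a large fraction when most values are BLOQ. Its absolute error stays below f·LLOQ. At f = 0.75 in the illustration the 7.8 mean is 0.35 to 0.64 LLOQ, which 7.3 would print as BLQ.
- The 7.8 rule is guaranteed closer only when Mq is at least 2 LLOQ, and late visits may not meet that.
- The bullet on a quantifiable value after two BLOQ values can lower a mean and lies outside the n/(n-k) relation. It is a separate point: without a slope to fit, it has no evident purpose.
- The leading-BLOQ conflict bites only if at least half, but not all, of the subjects are quantifiable at the one-hour sample; below half, 7.3 prints the geometric statistics as NC.
- The BLQ display still works at baseline and early visits, so the misfit with 7.3 is confined to visits where BLOQ values are set to missing.
- The reach is small. Both figures in 11.1.5 stop at Day 57, and the SAP's list of figures has no full-course PK plot. Individual concentrations are listed, 7.3 already reports the number above the quantification limit, and excluded data are flagged. Flagging helps a reader detect the choice, but it neither corrects the mean nor tells a programmer which rule to apply.

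**Conclusion.** The concern holds. The SAP gives two incompatible treatments of the same records in the only summary table defined in 11.1.4 for a secondary endpoint. If the 11.1.3 set-to-missing BLOQ bullets are applied, each affected visit mean is biased upward. The direction, the n/(n-k) ratio and the bounds in step 4 follow from algebra; the percentages in step 5 rest on the lognormal assumptions stated there. The actual size cannot be computed, because the documents give no LLOQ, half-life or expected BLOQ share. If 7.8 governs, this upward bias is absent, but the text remains ambiguous. The effect is limited to descriptive PK summaries, mainly at late follow-up visits. Individual data, population PK and the primary safety endpoint are unaffected.

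**What to change.** - State in 11.1.3 that 7.8 governs descriptive statistics and mean plots at every time point, including leading BLOQ values, with LLOQ/2 for geometric statistics.
- Keep every sampled subject in n, show the number quantifiable, and state that the 50% rule in 7.3 uses that n.
- Delete the two bullets that set BLOQ values to missing, or confine them to terminal-slope estimation should any be done.
- Separately, keep a quantifiable value that follows two BLOQ values in the summaries unless the PK Data Review excludes it with a documented reason.

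The cost is SAP wording only. Arithmetic means at affected visits will be low by less than the LLOQ, and some late cells will read NC or BLQ.
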